The patient will come to the obstetric (OB) pre-operative holding area where we will obtain her medical history, perform a physical exam and consent her for the cesarean delivery. The patient will have already spoken with a study coordinator and/or PI/Co-I more than one day prior to arrival regarding potential participation in the study. The patient will be approached by one of the study team members (anesthesiologists). We will review the consent form, explaining that itching is a common side effect of the intrathecal morphine and we are trialing a medication that would prevent the itching. If the patient agrees to participate, we will obtain signed consent, contact the study coordinator to be prepared for questionnaires post-procedure and then obtain a blinded syringe from pharmacy for the treatment. [name] will randomize the patient for the study to determine which medication the mother will receive using a stratified randomization design generated with MAPLE software.

The patient will then go back to the operating room when it is her operative time, and we will perform the spinal with bupivacaine, morphine and fentanyl, which is standard at our institution (see standard of care medications below). Once the spinal is confirmed to be adequate, the surgical team will be called in to perform the procedure. Once the baby is delivered and the procedure is completed, we will inject the blinded syringe of medication into the patient's left thigh since she will still be numb from the spinal. When the patient arrives to the PACU, we will assess the 4 variables 1 hour after medication is given in PACU and then between 4-5 hours post-op and at 24 hours post-op (+/- 2 hours). All evaluations will be done in person or by phone call from study coordinator.

If patients are still reporting pruritis that is not controlled, the rescue treatment will be butorphanol 1mg IV q3h, as this is the current regimen at our institution.

Treatment/Therapy

The treatment will consist of a blinded syringe of 1cc clear liquid (blinded to patient and physician – only pharmacist will know what it contains). This injection will be given in the left thigh after the cesarean delivery is completed.

Contents of syringe: (either)

- 1cc 0.9% Sodium Chloride (placebo)
- 1cc 25mg/ml Promethazine (study medication)

Extra studies/procedures required

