| Final Evaluation of variables (Phone call from coordinator) | | | | 24 h |

STATISTICAL METHODS, DATA ANALYSIS, AND INTERPRETATION:

Our plan is to recruit 50 patients for each arm of the study. With 50 patients on placebo and 50 patients on Phenergan, there will be a greater than 80% chance of detecting a significant difference of 20% or more at a two-sided 0.05 significance level. This assumes that severe itching occurs in 50% of patients and Phenergan reduces this proportion to 20%.

We will use Fisher's exact test to compare groups on severity of itching. We will also use Wilcoxon's rank sum test to compare groups on degree of itching as measured by the ITCHYQUANT. [name], the study biostatistician, will perform all statistical analyses.

DATA STORAGE AND DE-IDENTIFICATION PLANS:

The original, hard-copy signed informed consent forms and rhythm strips will be stored within the locked Anesthesiology research office and will remain with the Principal Investigator for at least 7 years. Data will be entered into an Excel spreadsheet kept on a password-protected and encrypted computer and retained by the Principal Investigator for at least 7 years.

Patients will be de-identified. No names, MRN's, or other identifying information will be stored in the spreadsheet. Pain, itching, sedation and nausea/vomiting will be collected at three intervals by a study coordinator and added to the de-identified spreadsheet. Age group, medical conditions such as diabetes and pre-eclampsia as well as BMI groups, will be used to determine confounders in the data. None of this collected information will be used to identify the patients.

7. Potential Risks:

Subjects will be given clear verbal and written instructions to contact [name] in the Department of Anesthesiology with questions or concerns regarding their study participation. If a patient experiences an injury that is directly caused by this study, they will receive professional medical care at the University of Florida. No other compensation is offered. Any adverse events will be reported to the

IRB using the standard adverse events reporting website and on continuing reviews (depending upon severity, as defined by the IRB).

1. Sedation (study variable). Promethazine can cause sedation which will be studied.
2. Concern for QT prolongation on the ECG causing cardiac arrhythmias. QTc evaluated on patient monitor, rhythm strip to be printed off and saved in research binder with QTc labeled clearly.

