3. Respiratory depression
4. Painful injection site once spinal wears off. Patients will be given the injection while spinal anesthesia is still working to prevent pain during injection.
5. Tissue damage at site of injection
6. There is the risk of loss of confidentiality. The following procedures will be done to maintain confidentiality: written, paper forms will be kept in the locked Anesthesia Research Office. Computerized and de-identified records containing personal health information will be stored on password-protected and encrypted computers.

Routine medications that are provided to patients participating in the study may be provided to you. These are part of normal clinical care. The participant will be responsible for any deductible, co-insurance, or co-payments. Some insurance companies may not cover costs associated with research studies or research-related injuries. If the participant is injured as a direct result of participation in the study, only professional services received from any University of Florida Health Science Center healthcare provider (physicians, physician assistants, nurse practitioners, dentists or psychologists) will be provided without charge. Any other expenses, including Shands hospital expenses, will be billed to the subject's insurance provider or the subject themselves.

Safety Endpoint

During the study, we will log our adverse events. If the incidence for adverse events is greater than expected we will review the study design as a team to decide if we should proceed with the study or stop the study. If we have an increase incidence of serious injection site reactions, we will review whether the medication or placebo is causing the injection site reaction. If any major adverse reactions occur we will have a meeting with the investigators to address if this was an unanticipated or potentially expected event given the expected incidences.

8. Potential Benefits:

The potential benefit of this study would be to find a prophylactic treatment for intrathecal opioid pruritus. The patients would undergo minimal risk with an IM injection in attempts to decrease one of the major side effects of intrathecal opioids. The study will benefit future women undergoing cesarean section as we could give intrathecal morphine for post-op pain control with less side effects.

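### Respiratory depression is a named risk, but no scheduled variable is respiratory; it is left to adverse-event logging with no stated definition, collection method or by-arm summary, so an absence of reports could not show respiratory safety.

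*Combined protocol and SAP*

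**What the plan says.** Section 7 (Potential Risks) numbers the risks of taking part. The third entry is, in full, "Respiratory depression". Two other entries in the list come with a measurement. Sedation is handled as an outcome: "Sedation (study variable). Promethazine can cause sedation which will be studied". For QT prolongation the plan says: "QTc evaluated on patient monitor, rhythm strip to be printed off and saved in research binder with QTc labeled clearly".

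The scheduled follow-up data are fixed in section 6. Under Data Storage and De-identification Plans: "Pain, itching, sedation and nausea/vomiting will be collected at three intervals by a study coordinator". Under Patient typical day: "we will assess the 4 variables 1 hour after medication is given in PACU and then between 4-5 hours post-op and at 24 hours", the last with a window of 2 hours either way. On the mode of contact: "All evaluations will be done in person or by phone call from study coordinator". The Table of Study Events labels all three evaluations as phone calls.

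Unscheduled safety information is covered in section 7. Under Safety Endpoint: "During the study, we will log our adverse events". The team then reviews the study if adverse events exceed expectation, looks separately at serious injection-site reactions, and meets after any major adverse reaction. The same section also has adverse events reported to the IRB.

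**The concern.** The protocol names a risk and then schedules nothing that would observe it. Sedation on the RASS is the nearest scheduled item, but it measures alertness, not breathing. A phone contact cannot measure respiratory rate or oxygen saturation, and nothing is scheduled between about 5 and 22 hours.

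What remains is the log. The plan does not say what counts as respiratory depression, who looks for it and when, what incidence is expected, or whether adverse events will be compared or tabulated by arm. Two things follow.

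- A report with few or no respiratory entries could not be interpreted, because a reader could not tell whether events were absent or simply not looked for.
- The review rule that depends on incidence has, for this risk, neither a systematic count nor a stated expected rate to compare it with.

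This matters because the protocol looks ahead to wider use of the approach. Section 3 hopes for more use of intrathecal narcotics, and section 8 foresees further studies of the spinal morphine dose and adoption outside obstetrics. All women are listed to receive intrathecal morphine and fentanyl, so later users will want to know what was seen on breathing in each arm.

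**Working it through.** **1. Risk against measurement.** Setting section 7 beside the data described in section 6:

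| Named risk | Measure in the plan |
|---|---|
| Sedation | RASS at three contacts |
| QT prolongation | Monitor QTc and saved rhythm strip |
| Respiratory depression | None beyond the general adverse-event log |
| Injection-site harm | Log, plus its own review rule for serious reactions |

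The procedures, the events table and the statistical section contain no respiratory rate, oxygen saturation or respiratory event item.

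**2. The plan's own figure.** The statistical section gives 50 women per arm, two-sided 0.05, and more than 80% power for severe itching of 50% against 20%. By the pooled normal approximation, with mean proportion 0.35:

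z = [0.30 × √50 − 1.96 × √(2 × 0.35 × 0.65)] / √(0.50 × 0.50 + 0.20 × 0.80) = (2.121 − 1.322) / 0.640 = 1.25, so power is 89.4%.

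Exact enumeration of Fisher's test gives 85.3%. The figure reproduces for these two rates. The sample size was set by itching, and the documents give no rate for respiratory depression. The event rates in steps 4 and 5 are therefore assumptions.

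**3. What zero events could exclude, with complete capture.** The upper limit for 0 of 50 is 1 − α^(1/50).

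- One-sided 95%: 1 − 0.05^(1/50) = 5.8%
- Two-sided 95%: 1 − 0.025^(1/50) = 7.1%

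With incomplete capture the true rate compatible with an empty log is higher. The documents do not allow the size of that shift to be estimated.

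**4. Chance of seeing any event.** At an assumed true rate of 1%, it is 1 − 0.99^50 = 39% in one arm and 1 − 0.99^100 = 63% in both. At 5% it is 92% and 99%.

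**5. What a comparison of counts could show.** For x events against 0, with 50 per arm, the two-sided Fisher p-value is 2 × C(50,x) / C(100,x).

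- 5 against 0: p = 0.056
- 6 against 0: p = 0.027

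So at least 6 against 0 is needed. Fisher power at 50 per arm is 2.4% for an assumed 1% against 5%, and 27% for 1% against 10%. For 1% against 5%, 80% power needs about 285 per arm (normal approximation).

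**The case against.** The strongest reply is that recognised events do have a route. They can enter the log, one major reaction is enough to convene the investigators without any excess in incidence, and adverse events go to the IRB. The women are in-patients, and the investigators routinely work in the obstetrics unit. Respiratory safety is not among the aims in section 5. All of this stands, and it limits the point to systematic ascertainment and reporting.

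A reader might infer four stronger things that the documents do not support.

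- *That the log takes only unprompted reports.* The plan does not say how the log is filled. The gap is that the method is not stated.
- *That the safety review can be triggered only by an excess of events.* The meeting after a major reaction is a second trigger and needs no excess.
- *That the missing item is why the trial cannot say whether promethazine depresses breathing.* With 50 per arm, step 5 shows that a scheduled yes/no item would not settle that question either, unless the difference were very large.
- *That the protocol plans to claim respiratory safety.* It does not. The risk lies in how silence might later be read.

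It is also fair to say that definitions, collection method and by-arm summary are missing for adverse events in general. Respiratory depression is the sharpest case because it is named as a risk and has neither a measure nor a rule of its own.

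**Conclusion.** The point holds in a limited form. A risk that the protocol itself names has no respiratory item in the scheduled data and depends on a log with no stated definition, collection method or by-arm summary. An absence of reports could not be read as evidence of respiratory safety. Even if every event were captured, 0 of 50 would exclude only rates above about 6 to 7%.

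Those limits rest on the planned 50 women per arm and on complete capture, which the plan does not secure. They describe what the sample size allows; they do not measure how many events the log would miss. The itching analysis is unaffected. The change is worth making because it is cheap, and because the analyst could not recover the information afterwards from the planned dataset.

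**What to change.** At the final contact, have the coordinator copy the following from the routine record, for Time 0 to the time of that contact and in the same way in both arms:

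- any supplemental oxygen, any naloxone and any airway support, each as yes/no;
- the lowest respiratory rate and the lowest oxygen saturation, where charted.

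Record the time of the contact. With its 2-hour window it may fall at 22 hours, so the period should not be described as a full 24 hours. Values that were not charted should be reported as missing.

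Report the yes/no items by arm as counts with exact 95% intervals, and the vital signs as median and range by arm. Make no formal safety claim. Include the yes/no counts in the Safety Endpoint review.

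The cost is a few data fields and minutes of chart review per patient by existing staff. The main weakness is dependence on routine charting, which the protocol does not state; the sponsor should confirm that these fields are charted before relying on them. No clinical threshold and no change in care is proposed.

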Hypothesis: Prophylactic intramuscular promethazine does not decrease pruritus in post-partum females that received 100mcg intrathecal morphine.

Alternate Hypothesis: Prophylactic intramuscular promethazine does decrease pruritus in post-partum females that received 100mcg intrathecal morphine.

Pruritus will be quantified by the ItchyQuant Scale, developed and validated by CG Haydek as seen below.⁹

Secondary Analysis

- Promethazine does not increase sedation compared to placebo (RASS scale)
- Promethazine does not increase pain compared to placebo (DVPRS scale)
- Promethazine decreases nausea and vomiting (rated as none, mild, moderate, severe)

6. Research Plan:

Inclusion criteria:

1. Pregnant adult female patients of at least 18 years of age consenting to a cesarean birth;
2. Willing to consent to study.

Exclusion criteria:

1. Male patients;
2. Incarceration;
3. Inability to communicate with the investigators;
4. Allergies to any medications used in the study;
5. Possessing any contraindication to spinal anesthesia (lack of consent, elevated intracranial pressure, preexisting neurological disease, thrombocytopenia/coagulopathy, hypovolemia, infection at the site of the procedure);
6. Patients with an already prolonged QTc (>500 ms)
7. Any reason an investigator believes study participation would not be in the best interest of the potential subject.

DESIGN

STUDY PROCEDURES

Recruitment

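### Injection-site reactions have their own safety review trigger, but no scheduled contact asks about the site, so the count rests on volunteered reports and may run low (minor, cheap to improve)

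*Combined protocol and SAP*

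**What the plan says.** Section 7 (Potential Risks) names two local harms of the injection. One is "Painful injection site once spinal wears off" and the other is tissue damage at the site.

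The Safety Endpoint paragraph of the same section has three triggers:
- Overall incidence: "If the incidence for adverse events is greater than expected we will review the study design as a team", with a decision whether to proceed or stop.
- Site reactions: "If we have an increase incidence of serious injection site reactions", the team will look into which of the two injections, drug or placebo, is responsible.
- Any major adverse reaction, which leads to an investigators' meeting.

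On how events are found, the protocol offers two routes. The Safety Endpoint says "During the study, we will log our adverse events", without saying who asks, what is asked or over what period. The opening of Section 7 says "Subjects will be given clear verbal and written instructions to contact" the anesthesiology department with questions or concerns.

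The scheduled data collection is narrower. Under Data Storage and De-identification Plans, "Pain, itching, sedation and nausea/vomiting will be collected at three intervals by a study coordinator". Patient typical day and Recording data responsibilities agree: four variables at 1 h, 4-5 h and 24 h (+/- 2 h), in person or by telephone. The Table of Study Events shows all three as telephone calls. Both arms receive a 1 mL injection in the left thigh while the spinal is still working.

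**The concern.** A rule that acts on an incidence, and then asks whether drug or placebo is responsible, needs the event looked for in the same way in every patient. Here it is not looked for at any scheduled time. Two other named risks are handled differently: sedation is a study variable, and QTc is read from the monitor and kept on a labelled rhythm strip. Injection-site harm has a review rule but no scheduled measurement.

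What is at stake is the quality of the count that goes to the safety review, and the local-tolerability statement the trial can make at the end. With only 50 patients on promethazine the expected number of cases is small, so a few unreported ones could change the picture.

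**Working it through.** **1. The plan's own figure.** There is none on this point. The documents state no expected site-reaction rate, no definition of a serious reaction, no threshold for an increase and no reporting fraction. The only numerical input is 50 patients per arm (Statistical Methods).

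**2. Does any scheduled step capture the site?**

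| Contact | Variables recorded | Site question or inspection |
|---|---|---|
| 1 h (PACU) | pain, itching, sedation, nausea/vomiting | none stated |
| 4-5 h | same four | none stated |
| 24 h (+/- 2 h) | same four | none stated |
| after 26 h at the latest | no contact scheduled | none stated |

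The protocol expects site pain to appear only after the block recedes, so the 1 h contact could miss it even with a question. The 4-5 h and 24 h contacts are the useful ones. What remains is the log and the instruction to make contact. Both are passive.

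**3. What passive capture could cost (illustration, all rates assumed).** Let r be the true site-reaction rate on promethazine and c the fraction that reaches the log. Then the expected number logged is 50rc, and P(at least one logged) = 1 - (1 - rc)^50.

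| r | c = 1 | c = 0.5 | c = 0.25 |
|---|---|---|---|
| 2% | 1.0 expected; 64% | 0.5; 39% | 0.25; 22% |
| 5% | 2.5; 92% | 1.25; 72% | 0.6; 47% |
| 10% | 5.0; 99.5% | 2.5; 92% | 1.25; 72% |

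For example, r = 5% and c = 0.5 gives 1 - 0.975^50 = 0.718. The loss shrinks as c nears 1: with r = 5% and c = 0.9, 1 - 0.955^50 = 0.90, against 0.92 with full capture.

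The table describes reactions of any grade. It is not the chance that the Safety Endpoint rule operates. That rule concerns an increase in serious reactions, and without a threshold its chance of operating cannot be calculated.

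**4. Could thigh pain distort the pain outcome?** DVPRS has no body site attached in the Secondary Analysis list. If a share q of promethazine patients, over and above saline, has thigh pain that adds d points, the arm means differ by qd. With q from 10% to 40% and d from 1 to 3, the shift is 0.1 to 1.2 points. The standard error of the difference is SD x sqrt(2/50), which is 0.4 for an assumed SD of 2 and 0.5 for an SD of 2.5. The probability of p < 0.05 in the direction of more pain on promethazine is about Phi(shift/SE - 1.96):
- shift 0.1: about 4%
- shift 0.4 (20% x 2 points): 12% to 17%
- shift 1.2: 67% to 85%

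The distortion is material only toward the upper end of these assumptions.

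**The case against.** The best defence is that capture is passive but not absent. Participants are in-patients, the 1 h assessment is in PACU, contacts may be face to face, an adverse-event log exists and patients are told how to report concerns. The rule concerns serious reactions, and significant tissue injury in a hospitalised woman is likely to be noticed without prompting. This stands. It means that the likely loss is concentrated in non-serious reactions, and that under-counting is a possibility rather than an established fact.

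A reader might infer three stronger things that the documents do not support.
- That injection-site harm governs the Safety Endpoint. It is one of three triggers, and the proceed-or-stop decision is attached to overall adverse-event incidence. The site-reaction sentence leads only to a review of cause.
- That no one will ask about or look at the thigh. The protocol schedules no such step, but it does not rule out clinical staff doing so.
- That the pain outcome is compromised and should be restricted to the incision. Both arms are injected, so only a drug-specific excess matters. Any bias would run against promethazine and could not create a false finding of no added pain. The stated aim concerns pain compared with placebo without limiting it to the wound, so a pain score that includes pain from the injection is a legitimate reading. An incision-only score would change that aim.

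After these concessions, a review rule is still left depending on an incidence that the plan does not collect systematically.

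**Conclusion.** The gap is real and minor. Local harm is a named risk with its own review trigger, yet none of the three scheduled contacts includes a site item. Site reactions may therefore be under-counted, chiefly the non-serious ones. That they will be under-counted, or by how much, cannot be shown from the documents: every rate in the working is assumed, and serious reactions probably have capture well above the lower fractions used there. The conclusion rests on reading the four listed variables as the whole of the contact form, which the relevant sections support consistently. Neither the sample size nor the stated pain aim needs to change.

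**What to change.** At the existing 4-5 h and 24 h contacts, ask every patient in both arms one fixed question about the left-thigh injection site, covering pain, redness, swelling and skin change, each graded none, mild, moderate or severe. When the contact is in person, look at the site as well. Enter the answers in the adverse-event log so that they can be tabulated by arm for the Safety Endpoint review, with the coordinator remaining blinded.

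Keep the overall DVPRS as the pain outcome. The site item can then help to interpret any pain difference between arms.

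The cost is one line on the contact form, about one minute per contact, and more minor complaints logged in both arms. Two limits remain. Reactions that appear after the 24 h contact would still be unsolicited, and the rule would still lack definitions of serious and of increase, which the investigators could add to the same paragraph.
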